Protocol Title: SCH: Context-aware Freezing of Gait mitigation in real-world setting

Identification: **NCT Number**NCT04746846

Unique Protocol IdHM20020085

PI: [name]

Version Date: 6/13/2023

IRB approval date: 7/31/2023

Full Study Title: SCH: Context-aware Freezing of Gait mitigation in real-world setting

PROTOCOL DOCUMENT

4.2. Study Design:

4.2.a. Narrative Study Description

Design. This is a single site clinical trial involving 3 tasks with the purpose of development and testing feasibility of a device. In total, 32 participants with Parkinson's disease (PD) who experience freezing of gait (FoG) will complete this 3-year study. We will enroll up to 50 participants to account for screen fails and withdrawals.

Procedures. All procedures are performed exclusively for research purposes. After obtaining consent from the PD patient, a member of the research team will administer the Montreal Cognitive Assessment (MoCA) test to determine cognitive eligibility (must score at 21 or higher to be eligible). If the participant is eligible, they will be assigned a code number, then asked to complete a demographic form, a physical performance test (10-Meter Walk test) and the remaining scales in Table 1, to capture relevant physical and neuropsychological covariates.

Table 1. Physical and Neuropsychological Scales (total participant time for all the below measures is 30 minutes).

Factor	Validated Scale
Cognition	Montreal Cognitive Assessment [1]
Fatigue	Parkinson's Disease Fatigue Scale [2]
Balance Confidence	Activities-specific Balance Confidence (ABC) scale [3]
Fear of Falling	Falls Efficacy Scale-International [4]
Quality of Life	Parkinson's Disease Questionnaire-8 [5]
Freezing of Gait	New Freezing of Gait questionnaire [6]
Nonmotor Symptoms	MDS-UPDRS part 1 questionnaire [7]
Walking Speed and Step Length	10 Meter Walk Test [8]

All 32 participants will be screened with the same inclusion and exclusion criteria described in section 2.2 above. All will undergo the same consenting procedure described above. Each study participant will wear a safety belt and have trained spotters to deter falls. The specific procedures for each of the 3 tasks are as follows:

In Task 1, a convenience sample of five participants will be recruited for CNN model training. For each patient, we plan to collect data for 2.8 hours, among which at least 17 minutes will be FoG data. Each participant will be asked to wear one UG motion sensor (watch like device with a soft band) around each ankle to collect raw data that will be used to detect FoG and develop models. They will be video-taped (for the purpose of validating the FoG detection models) as they walk each of the five 5-meter FoG triggering courses illustrated in Figure 1. All assessments in Task 1 will be performed on PD participants who are OFF their PD medications (overnight washout) to maximize the amount of time spent in FoG, thereby minimizing the length of evaluation time [19]. It is common in both clinical practice and research studies to bring PD patients in for assessments off their PD medications; thus, this is not anticipated to be a barrier to recruitment. The 6 participants in Task 1 will not participate in Task 2 & 3.

Task #1: Each subject is expected to spend up to 4 hours in the clinical lab, one visit. This can be divided into two sessions if the subject prefers.

[figure not shown]

Figure 1: Five FoG Triggering Scenarios shall include a 5-meter walking path with one of 5 triggers inserted into the path: (A) walking through a narrow passage, (B) turning 540 degrees, (C) approaching a destination (e.g., chair), (D) walking while dual tasking (e.g., performing a verbal fluency challenge while walking), and (E) a time sensitive task such as walking through an elevator door before it closes.

Table 2. Task 2 Neuropsychological Scales (total participant time for all the below measures is 88 to 118 minutes).

Anxiety	State Trait Anxiety Inventory (STAI- State & Trait) [9] Positive and Negative Affect Schedule (PANAS-State) [10] Semi-structured qualitative interview Salivary Alpha-Amylase [11-13]
Sleep	RegUlarity, Satisfaction, Alertness, Timing, Efficiency, and Duration (RU SATED) [14] Insomnia Severity Index (ISI) [15] Pittsburgh Sleep Quality index (PSQI) [16] Actigraph Consensus Sleep Diary [17]
Self-Efficacy	General Self-Efficacy Scale (GSE) [18]
Illness Self-Concept	Illness Self-Concept Scale (ISCS) [19-20]

The goals of **Task 2** are to (1) determine the optimal frequency and vibration settings to mitigate freezing of gait (FoG) and (2) explore the role of neuropsychological factors such as sleep and anxiety in FoG outcomes (see Table 1 & 2). Thus, response surface methodology is proposed. Specifically, a central composite design (CCD) [38] will be used to determine the best dose of vibration (frequency and amplitude) for each of five common triggers for FoG (Figure 1). Estimating the response surface requires only a small sample of human participants, e.g., one participant for each design point with five repeats at the center point. For the current project, a convenience sample of only 13 participants with PD who experience FoG in at least two of the scenarios, confirmed by a neurologist will be needed. The 13 participants will be asked to walk through each of five, 5-meter walking courses that will each include one of the triggering scenarios. Each of the 13 PD participants with FoG will be randomly assigned to one of 9 different *ff* and *va* settings as prescribed by the CCD. In the current case, the goal is to estimate the *ff* and *va* settings that will maximize the difference between the baseline (no vibration) and post-treatment time spent in a FoG state for each of the 5 triggering scenarios individually and in total. Measurements will be taken once at baseline and again in triplicate as they walk the paths wearing the FoG detection/vibration device.

Additional activities for Task 2 participants:

Visit #1: After the consenting process is completed, a sample of saliva will be collected (see procedure below) to measure salivary alpha amylase levels at baseline. The UG device and PDVibe3 will be placed on the participants who will then perform a 10-meter walk test on site and a baseline walk of the five triggering

scenarios. They will complete the questionnaires/scales listed in tables 1 and 2. Participants will then be instructed on how to wear the actigraph device on their dominant wrist (Actigraph GT9X Link) to collect objective sleep data for up to 14 days prior to their Visit #2. They will also be instructed on how to complete the sleep diary during the same time period during which the actigraph is collecting sleep data. Visit #1 will last approximately 90 minutes.

Participants will wear the ActiGraph GT9X Link for up to 14 consecutive, 24-hour days beginning at baseline, pre-intervention. Actigraphs are devices that are worn on the dominant wrist and contain a built-in accelerometer that records movements in order to estimate sleep parameters, including total sleep time, sleep-onset latency, wake after sleep onset, and sleep efficiency. Sleep data will be analyzed using the ActiLife 6.0 data analysis software platform and bedtime and waketime will be verified via sleep diary-reported data. Prior to receiving the actigraph, participants will receive verbal instructions regarding the purpose of the actigraph (i.e., that the actigraph records movement to estimate sleep parameters) as well as appropriate use (i.e. should be worn on the dominant wrist at all times for up to fourteen consecutive days unless bathing, swimming, etc.). Participants will be provided with moleskin as necessary to minimize risk of skin abrasion. Participants will be encouraged to reach out to study personnel with any questions or concerns related to wearing the actigraph device while at home.

Participant saliva will be collected with the aim to assess salivary alpha amylase, a biomarker shown to be a reliable indicator of anxiety and stress in individuals with PD. Saliva sample collection will occur three times over the course of Task 2- at baseline (Visit #1), pre walking tasks and post walking tasks (Visit #2). Saliva will be collected using a passive drool method, a method of saliva collection that requires participants to lean forward and allow saliva to naturally pool into the collection vessel rather than actively spitting. This method of saliva collection allows for whole saliva to be collected, avoiding localized salivary secretions and providing for a more consistent biospecimen. Saliva samples will be collected utilizing Salimetrics Saliva Collection Aid, a mechanism which fits securely into a collection vial designed to reduce sample foaming and facilitates direct sample collection and storage. Samples will be refrigerated within 30 minutes of initial collection and frozen at or below -20 degrees Celsius within 4 hours of collection. Samples can be stored for up to 6 months and will be stored until all participant samples are collected, at which point an alpha amylase assay will be run. Prior to participating in saliva collection, participants will receive verbal instructions on how to correctly provide a saliva sample. Participants will be advised to avoid eating a major meal for at least one hour and will be asked to rinse their mouths thoroughly with water 10 minutes prior to collection.

Visit #2: In addition to what is described in Task #1 above, saliva samples will be collected from participants before and after their participation in the walking tasks. They will also complete 2 surveys, the STAI-State and PANAS-State after they finish walking. The sleep diary that was filled out at home will be collected from participant and actigraphy will be retrieved. Following completion of walking tasks, participants will be invited to schedule a time to engage in a semi-structured qualitative interview virtually or by phone. Visit #2 will last approximately 120 to 180 minutes).

Visit #3: Participants will engage in a semi-structured interview via telephone or virtually according to participant preference. The interview will ask participants to reflect on and engage in discussion related to experiences of FoG; perceptions of the association between sleep, anxiety, and FoG; illness self-concept; mobility self-efficacy; general feedback about the interview and participation in the study overall (see submitted interview protocol document). Visit #3 will last approximately 30 to 60 minutes.

Participants will be ON their PD medications during this phase of testing. The study staff, except for the PC, will be blinded to the treatment allocation. The PC will be setting the VibeForward vibration parameters (*ff* and *va*) for each participant according to a randomized list generated by the co-I and biostatistician, Dr. [name] All participants will wear safety belts and have trained spotters to deter falls. Participants will be asked to also participate in Task 3.

Task #2: Each subject is expected to spend up to 5 hours in the clinical setting, across three visits.

Updated 13JUN2023

Version 3.0

In Task 3 we will test the device at the optimal vibration setting in a “real world” setting. Due to the innovative nature of studying this device in a real-world environment, no pilot data exists from which to run a traditional power analysis. However, Van Belle proposed that a minimum of 12 observations should be used to calculate confidence intervals based on the t-statistic with $n - 1$ degrees of freedom. This rule is based on the fact that the half-width confidence interval for the mean decreases rapidly up to $n = 12$, at which point the decrease is less dramatic and the half-width curve begins to asymptotically decrease. Thus, in order to ensure the good estimates of the means and variances (pre- and post-) [39] a convenience sample of thirteen volunteers who have been diagnosed with PD by a neurologist and who exhibit FoG will be asked to participate in the testing of the device.

Participants will walk the pathway once without vibration (pre-treatment), and then three times with vibration (post treatment). They will be ON their medications. We will compare the differences in the duration and number of FoG episodes, time walking through the path, average stride length, and speed of walking. It is anticipated that “pre” versus “post” trials for each of these five variables will be compared using a paired t-test.

All participants in Task 3 will be described in terms of demographics, disease, and psychological characteristics as in Task 2. Detailed field notes will be made of observations from study staff and comments from subjects to record the extent and type of unpredictable challenges faced by each participant. Qualitative questions will be asked after each participant finishes the walking portion of the study. If a participant from Task 2 does not participate in Task 3, they will be replaced. The replacement will then complete the baseline walking portion and scales (Table 1) from Task 2 at a separate visit prior to completing Task 3. Patients from Task 2 will be reconsented for Task 3.

When the PC contacts participants who have already completed Task 2 to participate in Task 3, the PC will ask if they want to participate in a follow-up phone call with the interviewer they spoke with earlier. If yes, the interviewer will contact the participants and will share the main overall themes that surfaced from qualitative analysis of completed interviews. Participants will be asked (via phone, zoom, or in-person) to provide their feedback on these overall themes. Their feedback will then be incorporated into final analysis and interpretation of qualitative interviews. It is anticipated that this will take from 15 – 30 minutes. Participants can decline this portion of the study.

Participants in Task 3 will walk the 5 triggering scenarios (Figure 1) in a community setting (at the Short Pump Town Center) while wearing the UG device and the PDVibe3. Prior to walking in the community setting, participants will be consented and complete the questionnaires in Table 3 in a private VCU space (at the Short Pump Pavilion clinic).

Table 3. Physical and Neuropsychological Scales (total participant time for all the below measures is 30 minutes).

Factor	Validated Scale
Cognition	Montreal Cognitive Assessment [1]
Freezing of Gait	New Freezing of Gait questionnaire [6]
Motor Symptoms	MDS-UPDRS part 3 [7]
Walking Speed and Step Length	10 Meter Walk Test [8]
Fatigue	Rating of Fatigue Scale [21]

Task #3: Each subject that completed Task 2 is expected to spend up to 5 hours in the community setting (outside setting), and clinical setting, across two visits. Each subject that did not complete Task 2 is expected to spend up to 8 hours in the VCU clinical setting and an outside community setting, across two visits.

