to improve a variety of gait parameters in most PD patients using the “one size fits all” approach. In contrast, the proposed work in this NSF application is to determine the optimal vibration frequency (ff) and amplitude (va) parameters to mitigate FoG triggered by five different commonly encountered scenarios, using a closed loop system that will detect FoG. Thus, the vibration will only be used when it is needed.

[figure not shown]

Figure 8: Triggering scenarios shall include a 5 meter walking path with one of 5 triggers inserted into the path: (A) walking through a narrow passage, (B) turning 540 degrees, (C) approaching a destination (e.g., chair), (D) walking while dual tasking (e.g., performing a verbal fluency challenge while walking), and (E) a time-sensitive task such as walking through an elevator door before it closes.

To accomplish this goal, walking courses will be developed in the VCU physical therapy gym to mimic the five most common triggers of FoG [5]. Using response surface methodology employing a central composite design [38], we will determine the best dose of vibration (frequency and amplitude) for each of five common triggers for FoG (see Figure 8) using a small sample of human participants. To determine the optimal vibration frequency (ff) and amplitude (va) parameters for preventing or mitigating FoG in each of these scenarios, 13 participants with PD who experience FoG in at least two of the scenarios, confirmed by a neurologist will be recruited. Participants who participate in Task 1 are not eligible to participate in Task 2 or 3. Participants in Task 2 will be evaluated ON their medications. Participants will be asked to walk through each of five, 5-meter walking courses that will each include one of the triggering scenarios illustrated above. Measurements will be taken once at baseline and again in triplicate as they walk the path wearing the FoG detection/vibration device.

Each of the 13 PD participants with FoG will be assigned to one of 9 different ff and va settings as prescribed by the central composite design (CCD). The CCD, described below, is an elegant and efficient experimental design used in response surface methodology to estimate an optimal response. In the current case, the goal is to estimate the ff and va settings that will maximize the difference between the baseline and post-treatment time spent in a FoG state for each of the 5 triggering scenarios individually and in total.

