The CCD is specified by first defining a 2×2 factorial with four (ff , va) design points: (175, 0.55), (175, 0.75), (275, 0.55) and (275, 0.75) denoted in the plot by the solid dots (Figure 9). The design points are based on ff and va parameter settings C2 factors are capable of delivering (C2 factor datasheet) used in previous vibration research conducted by [name] (PI).

The four factorial design points are sufficient to estimate a first-order response surface that is flat (no curvature). In order to estimate a second-order response surface (or curvature in the response surface), the 2×2 factorial is augmented with axial points and multiple center points. Assuming a frequency range of 175 to 275 from the factorial portion, the axial points are defined as (154.29, 0.65), (295.71, 0.65), (225, 0.509) and (225, 0.791) denoted by the open dots emanating from the face of the cube. These axial points are chosen such that the design is rotatable, i.e., the prediction

[figure not shown]

Figure 9: The Central Composite Design

variance is constant on spheres around the center of the design. The number of center points (225, 0.65) denoted by "X") is chosen to be five to optimize estimate of the prediction variance and lack-of-fit. Thus, the full CCD with five center points will require 13 PD participants. To determine the optimal vibration frequency (*ff*) and amplitude (*va*) parameters for preventing or mitigating FoG, 13 participants will be randomly assigned to one of 9 different frequency (*ff*) and amplitude (*va*) settings as prescribed by the central composite design (CCD). Using response surface methodology, the response surface based on the baseline value minus the average of 3 post-vibration trials will be estimated yielding settings of frequency and vibration that will be the difference between the baseline and post-treatment time spent in a FoG state.

An overall optimum *ff* and *va* will be estimated using response surface methodology by fitting the following second order model:

$$y_i = \beta_0 + \beta_1 x_{1i} + \beta_2 x_{2i} + \beta_{11} x_{1i}^2 + \beta_{22} x_{2i}^2 + \beta_{12} x_{1i} x_{2i} + \varepsilon_{ij}$$

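### Task 2 gives each participant one vibration setting three times, so 39 vibration circuits yield only 13 between-person values; a planned incomplete-block list over the same nine settings would probably estimate the surface more precisely, by an amount that depends on variances the documents do not give.

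*Protocol*

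**What the plan says.** The Protocol (4.2.a, Task 2) and the SAP (Section 3, Task 2) describe the same design.

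- **Allocation.** The Protocol states "Each of the 13 PD participants with FoG will be randomly assigned to one of 9 different" frequency and amplitude settings, with "one participant for each design point with five repeats at the center point". The SAP agrees: "Each of the 13 PD participants with FoG will be assigned to one of 9 different ff and va settings", and later in the section it adds that the assignment is random.
- **Size.** The SAP states "Thus, the full CCD with five center points will require 13 PD participants".
- **Walks.** The Protocol states "Measurements will be taken once at baseline and again in triplicate as they walk the paths wearing the FoG detection/vibration device". The baseline walk is at Visit 1. Up to 14 days of actigraphy come before Visit 2, and the saliva schedule places the main walking tasks at Visit 2.
- **Response.** In the SAP, "the response surface based on the baseline value minus the average of 3 post-vibration trials will be estimated". The model index runs over the 13 participants.
- **Use.** The fitted optimum for each of the five scenarios and in total (six outcomes) is programmed into the device for Task 3. SAP Section 5 judges its usefulness by the relative width of its 95% confidence interval.

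Neither document gives a variance, a within-person correlation, a target interval width or a statement on carry-over for Task 2. Neither gives a reason for repeating one setting within a person.

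**The concern.** Averaging three walks at one setting reduces walk-to-walk noise. It leaves two other components in the error: differences between people in how they respond to vibration, and the noise of the single baseline walk shared by a person's three change scores.

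Both could be large here. Eligibility requires freezing in only two of the five scenarios, yet a surface is fitted for each scenario. If the one person at an outer setting does not freeze in a given scenario, the recorded change is near zero whatever the setting does. The baseline also appears to come from a different day than the vibration walks, so day-to-day fluctuation adds to the shared noise.

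At stake is the precision of the settings carried into Task 3. A poorly determined surface gives wide intervals for the optimum, and makes it more likely that the SAP's contingency plan decides the Task 3 settings instead.

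**Working it through.** A circuit here means one pass of the five courses.

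**1. The plan's own figure.** A two-factor central composite design with five centre points has 2² + 2×2 + 5 = 13 runs. The factorial half-ranges are 50 and 0.10, so the axial points are 225 ± 50√2 = 154.29 and 295.71, and 0.65 ± 0.10√2 = 0.509 and 0.791. All match the SAP. Circuits: 13 × 3 = 39. Values analysed: 13. Residual df: 13 − 6 = 7, of which 4 are pure error, all from the five centre participants.

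**2. Variances, planned design.** Take single-walk variance as 1. Let t2 be the between-person variance in vibration response on that scale, and b the variance of the single baseline walk. Each participant's value has variance t2 + 1/3 + b. The documents give neither t2 nor b, so both are assumptions. I use b = 1 (baseline as noisy as a vibration walk) and b = 0 (baseline noise fully removed by other means). The diagonal of (X′X)⁻¹ for the two linear, two quadratic and interaction terms, in coded units, is 0.125, 0.125, 0.144, 0.144, 0.250.

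**3. Variances, blocked design.** Use 13 participants with three circuits each and every design run used three times: 8 × 3 = 24 outer circuits and 5 × 3 = 15 centre circuits, total 39. With a participant effect fitted, the baseline and the person's general response both cancel from these five coefficients. An exchange search gave unit variances of 0.054, 0.055, 0.052, 0.056, 0.100, each multiplied by 1.

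One arrangement that attains this labels the factorial points a(−,−), b(−,+), c(+,−), d(+,+) and the axial points e(−√2,0), f(+√2,0), g(0,−√2), h(0,+√2). Every participant has the centre plus, in turn: cd, fh, ac, dg, eg, bg, eh, ah, bf, bd, af, e with a second centre, c with a second centre.

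**4. Ratio of standard errors, blocked to planned.** This is √[blocked variance ÷ (planned variance × (t2 + 1/3 + b))]. For the second linear term at t2 = 0 and b = 1: √[0.0551 ÷ (0.125 × 1.333)] = 0.575. Over the five coefficients:

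| | t2 = 0 | t2 = 0.5 | t2 = 1 |
|---|---|---|---|
| b = 1 | 52-58% | 44-49% | 39-43% |
| b = 0 | 104-115% | 66-73% | 52-58% |

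**5. Degrees of freedom.** 39 − 13 − 5 = 21 before order terms; 20 with a linear order term and 19 with a categorical one. The 95% t multiplier falls from 2.36 (7 df) to about 2.09. As 2.09 ÷ 2.36 = 0.89, coefficient intervals narrow by roughly a further 11%.

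**6. Sensitivity.**
- *Unplanned triples.* With b = 0, triples drawn at random give median ratios of 1.24 at t2 = 0, 0.94 at 0.25 and 0.78 at 0.5. The blocks need to be planned.
- *Carry-over fitted.* A person's three change scores have correlation (t2 + b)/(t2 + b + 1), which is 0.5 at t2 = 0, b = 1. With period and linear carry-over terms in the model, the error of the surface's shape still falls by 46% at correlation 0.5 and 30% at 0.3, against 48% and 32% without those terms.
- *Carry-over ignored.* Proportional carry-over of 20-40% with randomised order shrank the coefficients by about 7-13% and left the mean estimated optimum almost unchanged.
- *Person-by-setting variation.* If all shared variance is of this kind and makes up half the total, the gain is 30%.
- *Absolute height of the surface.* The gain is smaller than for its shape: 33% against 48% at correlation 0.5.

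**The case against.** **Carry-over.** This is the strongest objection, and it stands. A reader might infer that averaging three vibration walks already presumes no important carry-over, so that varying the setting costs nothing. The documents do not support that. With one setting per person, any carry-over is that setting acting on itself, and the average still describes it. Only a within-person design needs one setting not to affect the walk at the next. An order term detects a common trend, not setting-specific carry-over, and the documents give no washout data. The closed-loop device, which vibrates only when freezing is detected, limits exposure but does not settle the matter.

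**Source of the gain.** With b = 1 and t2 = 0, the whole gain comes from removing single-baseline noise. Baseline adjustment or more baseline walks could recover part of it without changing the allocation. This also stands, and is why both rows of the table are needed.

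**Bias.** A reader might infer that, with one person at each outer setting, the surface is biased. It is not: settings are randomly assigned, so person differences add noise, and the five centre participants provide a 4-df estimate of it.

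**Purpose.** The plan is a standard design in a study meant to develop a device and test feasibility. That is fair. The point concerns efficiency and does not show an error.

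**Conclusion.** The structure is certain: 39 vibration circuits are reduced to 13 between-person values for six coefficients, with one person at each outer setting. The design is valid but probably inefficient.

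The size of the gain is conditional. With equally noisy baseline and vibration walks, coefficient standard errors would fall by about 42-48% at t2 = 0 and 57-61% at t2 = 1. With baseline noise fully removed by other means, the blocked design is 4-15% worse at t2 = 0, about 27-34% better at t2 = 0.5 and 42-48% better at t2 = 1. A reader might want one headline percentage; the documents contain no variance components to support one.

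These figures assume well-chosen blocks and small or modelled carry-over. They concern the shape of the surface, which locates the optimum. I regard the change as a cheap improvement worth making if the team can defend the carry-over assumption.

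**What to change.** Keep the 13 participants, the nine settings, and one baseline plus three vibration circuits. Have the statistician prepare a planned incomplete-block list giving each participant three design runs in random order, one circuit each, with every run used three times. Because there are 15 centre circuits for 13 people, some participants must repeat the centre. Participants should be randomised to blocks.

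Fit the same second-order model to the 39 circuits for each outcome, with a participant effect and circuit-order terms (19-20 residual df). Prespecify a sensitivity analysis with a first-order carry-over term. Keep the baseline for reporting the absolute reduction in freezing.

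The cost is a Protocol and SAP amendment, and two device resets per participant by the coordinator, who already sets the parameters unblinded. Each person gives one circuit per setting instead of three (two at the centre where it repeats), and participants meet up to three settings instead of one. Whether that is acceptable within a visit is for the investigators and the IRB. The SAP should state the carry-over assumption openly. If the team cannot accept it, the allocation can stay, with the baseline made less noisy and the precision limits of 13 values stated.

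### Task 2 fits each response surface to a raw baseline-minus-vibration difference with no baseline term, which costs precision, and the entry rule does not secure five trigger-specific optima

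*Protocol*

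**What the plan says.** Protocol section 4.2.a (Task 2) seeks the settings that "maximize the difference between the baseline (no vibration) and post-treatment time spent in a FoG state for each of the 5 triggering scenarios". It calls for "13 participants with PD who experience FoG in at least two of the scenarios, confirmed by a neurologist will be needed". They are spread over a central composite design with "one participant for each design point with five repeats at the center point". Walks are scheduled as follows: "Measurements will be taken once at baseline and again in triplicate".

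SAP section 3 asks for the settings that give the largest fall in "time spent in a FoG state for each of the 5 triggering scenarios individually and in total", so there are six surfaces. It defines the response as the baseline value minus the average of the three vibration walks. The model has six coefficients: intercept, two linear, two quadratic and one interaction, all in frequency and amplitude. There is no baseline term, and no other model is given for single triggers. The Table 1 scales are only tabulated.

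SAP section 5 (Optimal dose evaluation) plans a 95% confidence interval around each of the six optima and judges their usefulness by its width. The optima are then programmed into the device for Task 3. The Vibration Dose Contingency Plan in SAP section 3 covers scenarios with no identified optimum, but does not say when an optimum counts as identified.

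On timing, the protocol's Visit 1 participants "will then perform a 10-meter walk test on site and a baseline walk of the five triggering" scenarios, then wear an actigraph "to collect objective sleep data for up to 14 days prior to their Visit #2". At Visit 2, "saliva samples will be collected from participants before and after their participation in the walking tasks". The SAP model was written for a single 2-hour session (SAP section 5).

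**The concern.** A person's FoG time cannot fall by more than that person's baseline FoG time. If benefit scales even roughly with baseline, the raw difference measures severity as well as vibration. Outside the centre, setting and person are the same thing: one severe participant, or one who does not freeze in that trigger, can raise or lower that part of the surface. Randomisation balances this over repeated trials, but not within one allocation of 13 people.

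The entry rule is a second gap. It counts triggers per person and sets no minimum of people per trigger. A participant without FoG in a trigger still supplies a value near zero, so the model runs on 13 rows, but that value says nothing about which setting works better.

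At stake is what goes into Task 3. Wide intervals will show that an optimum is weak, but not whether too few people froze or no setting stood out. Both lead to the same contingency.

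**Working it through.** **1. The plan's design reproduces.** Inputs from SAP section 3: factorial points at 175/275 and 0.55/0.75, centre (225, 0.65), five centre runs.
- Runs: 4 + 4 + 5 = 13, at 9 settings.
- Axial points: 225 ± 50√2 = 154.29 and 295.71; 0.65 ± 0.10√2 = 0.509 and 0.791. All match the SAP.
- Residual df: 13 − 6 = 7.

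**2. Leverage.** The diagonal of X(X'X)⁻¹X' is 0.625 at each outer point and 0.200 at each centre run (check: 8 × 0.625 + 5 × 0.200 = 6 coefficients). Illustration with assumed times: a 40% reduction at every setting gives 4 s for a 10 s baseline and 24 s for a 60 s baseline. If the 60 s person sits at an outer point and the other 12 have 10 s, the fitted value there is 4 + 0.625 × (24 − 4) = 16.5 s, although no setting is better.

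**3. Entry floor (no assumption needed).**
- Cells with FoG guaranteed by entry: 13 × 2 = 26 of 13 × 5 = 65.
- Average per trigger: 26/5 = 5.2 of 13; among the eight outer settings, 8 × 2/5 = 3.2.
- If all 13 qualify on the same two triggers, the other three have none.

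Share of possible placements in which the freezers alone identify the six-coefficient surface (all subsets of the 13 design rows, by matrix rank):

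| Freezers | ≤5 | 6 | 7 | 8 | 9 | ≥10 |
|---|---|---|---|---|---|---|
| Identifiable | 0% | 16% | 41% | 68% | 90% | 100% |

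**4. Effect of a baseline covariate when no setting is better.** The documents give no freezing rates or variances, so these inputs are assumed: lognormal severity with CV 1; reductions of 25–75% unrelated to setting; one baseline walk and three vibration walks; all 13 rows kept. 'Noise' means an 80% chance of freezing per walk, walk CV 0.5 and a separate visit factor with CV 0.5. The unit is the mean FoG time of a freezer. Median spread of fitted values across the nine settings:

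| Share freezing in the trigger | No noise: raw → adjusted | Noise: raw → adjusted |
|---|---|---|
| 40% | 0.57 → 0.14 | 0.82 → 0.33 |
| 70% | 0.77 → 0.24 | 1.27 → 0.56 |
| All | 0.80 → 0.31 | 1.64 → 0.71 |

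The largest cut is 1 − 0.14/0.57 = 75% and the smallest 1 − 0.56/1.27 = 56%. A re-run agreed within simulation error. The size of the 5% test for any setting effect was 5.6–7.2% raw and 5.8–8.8% adjusted, so neither fit shows gross inflation.

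**5. Effect on the optimum itself.** Chance that the fitted maximum lies within 0.5 coded units of an assumed true optimum, raw → adjusted:

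| True optimum (coded) | All freeze, no noise | All freeze, noise | 40% freeze, noise |
|---|---|---|---|
| (0.5, −0.5) | 34% → 73% | 7% → 8% | 4% → 3% |
| Centre | 55% → 97% | 19% → 12% | 23% → 5% |
| (1, −1) | 56% → 86% | 18% → 26% | 14% → 15% |

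Mean share of the design region inside a 95% region for the optimum: 0.89–0.96 falls to about 0.5 with no noise and everyone freezing, but 0.92–0.95 falls only to 0.85–0.90 with noise.

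**6. Cost.** Residual df go from 7 to 6. The t multiplier goes from 2.365 to 2.447, a ratio of 1.035, so intervals are 3.5% wider at equal residual SD.

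**The case against.** The strongest objection is that the covariate does little for what the plan reports. With noise, placement of the optimum hardly improves and is worse for an optimum at the centre. The clear gains need walks without noise, which a single baseline walk does not offer. The large interval gains (41–81% narrower over severity CV 0.5–1.5) are for a response contrast, outer setting minus centre, whereas SAP section 5 plans intervals around the optimum. This stands, and it limits the claim. The fall at the centre is mostly an artefact: with no setting effect at all, the raw fit still puts its maximum near the centre in 12–17% of runs, against 2–3% adjusted.

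It is also fair that differencing already removes a purely additive person effect, that one additive slope does not fully model a proportional benefit, and that part of the gain comes from error in the single baseline walk. In a separate check with no severity spread, a baseline term still raised hits from 44% to 93%. None of this argues for leaving the term out.

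Finally, Task 2 is feasibility work. The SAP foresees missing optima, uses interval width to judge them, and collects the data needed to count freezers. What remains missing is a stated rule that uses those counts.

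A reader might infer that the optima are systematically biased. Randomisation rules that out: average fitted setting effects under a flat truth were about zero. A reader might also infer that most participants will not freeze in a given trigger. The 26 of 65 is a floor, not a forecast.

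**Conclusion.** The point holds as a matter of precision and reporting, and should be fixed. The raw-difference model lets chance imbalance in severity into the surface at leverage 0.625 per outer participant, and a baseline value already collected would remove much of it. The 56–75% cut in spurious spread rests on the assumed inputs above. The leverages, the entry floor and the identifiability counts do not.

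The covariate should not be presented as a cure. With noise and everyone freezing, the adjusted spurious spread (0.71) still exceeds the mean benefit (0.40), and the 95% region for the optimum still covers 0.85–0.90 of the design. Nor does it repair sparse freezing. Five trigger-specific optima remain possible, but the entry rule does not ensure them.

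The gap between baseline and vibration walks is an inference, though a clear one: the protocol places a baseline walk at Visit 1 and walking tasks at Visit 2, but does not say in words that the vibration walks are at Visit 2, or whether a further no-vibration walk is done there.

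**What to change.** 1. In every response-surface model, add baseline FoG time in that scenario as a covariate (total baseline FoG time for the total outcome). Keep all 13 participants, and report the unadjusted fit as a sensitivity analysis. State which visit's no-vibration walk is the baseline.
2. State that entry does not ensure five trigger-specific optima with informative 95% intervals. For each trigger, report how many participants had baseline FoG and which design points they cover.
3. Label a trigger 'too few froze' when its freezers alone cannot identify the six-coefficient surface. This is always so with five or fewer, never with ten or more, and depends on placement in between. Report it separately from 'no optimum found' before the Vibration Dose Contingency Plan is applied. This is a minimum for identifying the surface, not a promise of useful precision.
4. Treat any analysis limited to freezers as a sensitivity analysis, because selecting on one baseline walk brings regression to the mean. With no device effect and an 80% chance of freezing per walk, it would show an apparent benefit of (1 − 0.8) × severity = 0.2 × severity.

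The cost is SAP text, one model term and one residual degree of freedom. No extra participants, visits or walks are needed, and the trigger-specific optima stay as planned outcomes. The drawback is that one baseline walk is a noisy covariate, which is why the freezer counts should accompany every reported optimum.
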